Serum phosphorus <1.0 mg/dL (<0.3 mmol/L) (life threatening consequences)	Discontinue patient from study drug.
Hyperphosphatemia	
Serum phosphorus > 5.5 – 7.5 mg/dL	Maintain dose level of BGJ398 and optimize phosphate lowering therapy as clinically indicated
Serum phosphorus > 7.5 mg/dL for more than 7 days despite maximal phosphate-lowering therapy Or , Single serum phosphorus > 9.0 mg/dL regardless of duration or dose of phosphate lowering therapy.  (Optimize/maximize dose and schedule of phosphate lowering therapy in accordance with package insert, country or institutional guidelines.)	Hold BGJ398 dose until resolved to serum phosphorus $\leq$ 5.5 mg/dL:Restart BGJ398 at the same dose level with maximal phosphate binder dosing if the patient did not receive maximal phosphate binder dosing for serum phosphorus $>$ 7.0 mg/dL for $>$ 7 days.
	Reduce one dose level of BGJ398 if the patient had received maximal phosphate lowering therapy for serum phosphorus > 7.5 mg/dL for > 7 days or if patient had a one-time serum phosphorus of > 9.0 mg/dL. Restart BGJ398 with maximal phosphate binder dosing.
	It is recommended that phosphate binder dosing continues during BGJ398 dose interruptions for hyperphosphatemia and that serum phosphorus values be monitored frequently, e.g. every 2-3 days.
	Phosphate binder dosing should be held during the week off BGJ398 therapy each cycle (Days 22-28) and during BGJ398 dose interruptions for nonhyperphosphatemia adverse events.
Serum phosphorus with life-threatening consequences; urgent intervention indicated (e.g., dialysis)	Discontinue patient from study drug
Hypercalcemia	
Serum calcium Grade 2	
 
Hold BGJ398 dose until resolved to Grade 1 or baseline:
 
if resolved within ≤ 7 days after suspending BGJ398, maintain dose level.
 

Worst Toxicity CTCAE v4.03 Grade (unless otherwise specified)	Dose Modifications any time during a cycle of therapy
	
 
if resolved between > 7 days and 14 days after suspending BGJ398, ↓ 1 dose level.
 
if not resolved within ≤14 days, discontinue patient from study treatment.
 

Serum calcium Grade ≥3	Discontinue patient from the study treatment
Nervous system disorders	
Neurotoxicity	
Grade 2	Omit dose of BGJ398 until resolved to CTCAE Grade ≤ 1, then ↓ 1 dose level of BGJ398. If not resolved within ≤14 days, discontinue patient from study drug.
Grade $\geq 3$	Discontinue patient from study drug treatment
GI disorders	
Pancreatitis	
Grade ≥ 2	Discontinue patient from study drug treatment
Diarrhea	
General Comment	Antidiarrheal medication is recommended at the first sign of abdominal cramping, loose stools or overt diarrhea
Grade 1	Maintain dose level of BGJ398, initiate anti-diarrheal treatment
Grade 2	
 
Hold dose of BGJ398 until resolved to CTCAE Grade ≤ 1
 
Optimize anti-diarrheal treatment.
 
For reoccurrence of diarrhea CTCAE Grade 2, hold dose of BGJ398 until resolved to CTCAE Grade ≤ 1, ↓ BGJ398 by 1 dose level
 

Grade 3	
 
Hold dose of BGJ398 until resolved to CTCAE Grade ≤ 1
 
Optimize anti-diarrheal treatment
 
↓ BGJ398 by 1 dose level
 
For reoccurrence of diarrhea CTCAE Grade 3, despite optimal antidiarrheal treatment, discontinue patient from study treatment.
 

Grade 4	Discontinue patient from study treatment.
Vomiting	
Grade 2 not controlled by optimal anti-emetic therapy	Hold BGJ398 doses until ≤ Grade 1, ↓ 1 dose level.

Worst Toxicity CTCAE v4.03 Grade (unless otherwise specified)	Dose Modifications any time during a cycle of therapy
	If not resolved within ≤14 days, discontinue patient from study treatment.
Grade 3 not controlled by optimal anti-emetic therapy or Grade 4	Discontinue patient from study treatment.
Eye Disorders (confirmed by ophthalmic examination)	
Retinal disorders	
Grade 2 central serous retinopathy and central serous retinopathy - like events	Hold BGJ398 until resolved to ≤ Grade 1 and continue ophthalmic evaluation  • If resolved within ≤ 14 days, ↓ BGJ398 by 1 dose level  • If resolved after > 14 days, discontinue BGJ398
Grade 3 central serous retinopathy and central serous retinopathy- like events and any other Grade 3 eye disorders	Hold BGJ398 until resolved to Grade ≤ 1.  If resolved within ≤ 14 days, ↓ BGJ398 by 1 dose level  If resolved after > 14 days, discontinue BGJ398
≥ Grade 1 retinal vein occlusion, Grade 4 central serous retinopathy and central serous retinopathy-like events, and Grade 4 other eye disorders	Discontinue patient from study treatment.
Other ocular/visual toxicity	
≥ Grade 3	Hold BGJ398 until resolution to ≤ Grade 1
	• If resolution within ≤14 days, ↓ 1 dose level
	• If resolved after >14 days, discontinue BGJ398
General disorders	
Fatigue	
Grade ≥3	Hold dose of BGJ398 until resolved to CTCAE Grade ≤ 1
	• If resolved within ≤ 7 days, maintain dose level of BGJ398.
	• If resolved after > 7 days, discontinue patient from study treatment.
Other clinically significant AEs	
Grade 3	Hold dose of BGJ398 until resolved to CTCAE Grade ≤ 1, then ↓ 1 dose level of BGJ398.  If not resolved within ≤14 days, discontinue patient from study treatment.
Grade 4	Discontinue patient from study treatment.
All dose modifications should be based on the worst preceding toxicity medical monitor or designee.	y. Patients may have a third dose reduction only with approval of a QED Therapeutics'

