# 6.1.2 Ancillary treatments

Phosphate-lowering treatment, including low phosphate diet and phosphate binding therapy such as sevelamer hydrochloride, should be implemented prophylactically with meals on the first day of study drug initiation and modified as clinically indicated throughout BGJ398 administration. Recommendations for treatment are provided in Table 5, but should be modified as per country or institutional guidelines.

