# Management of Hyperphosphatemia

Hyperphosphatemia is a recognized on-target effect of potent and selective inhibitors of the FGFR pathway. While on BGJ398, patients should avoid foods that are especially high in phosphate and, if possible, should restrict dietary phosphate to 600 – 800 mg/day. High-phosphate foods include dairy products; meats, nuts, and other high-protein foods; processed foods; and dark colas.

Patients who have experienced hyperphosphatemia should take a phosphate binder such as sevelamer, sucroferric oxyhydroxide, lanthanum carbonate, ferric citrate, etc. within 30 minutes of a meal on the day while taking BGJ398. Once the patient has had hyperphosphatemia, the patient should remain on a low phosphate diet, if possible, and take phosphate binder on the days BGJ398 is taken, even if the serum phosphorus is normalized. Unless otherwise specified by the local package insert or institutional practice, the following regimen should be used to manage hyperphosphatemia:

- For serum phosphorus > 5.5 7.5 mg/dL
  - Start sevelamer 800 mg three times a day with meals
  - Increase the dose of sevelamer up to 1200 mg every 8 hours
- For serum phosphorus ≥7.5 mg/dL
  - o Increase the dose of sevelamer up to 1600 mg (2 tablets per meal) every 8 hours
  - Consider adding acetazolamide two to three 250 mg tablets per day.

During the BGJ398 cycle, patients do not need to be on a low phosphate diet or take a phosphate binder during their 1-week off period unless serum phosphorus is not normalized. Other dose modifications are provided in Table 5, but should be modified as per country or institutional practice.

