Inclusion/exclusion criteria	D	5.2, 5.3, 7.1.2	X	X																
Relevant medical history/current medical conditions	D	7.1.2.3		X																
Diagnosis and extent of cancer	D	7.1.2.3		X																
Prior antineoplastic therapy	D	7.1.2.3		X																
Prior/concomitant medications	D	6.3		X	Continuous												X	X		
Physical examination	S	7.2.2.1		X	X		X	X		X	X	X	X	X	X		X			
Height	D	7.2.2.3		X																
Weight	D	7.2.2.3		X	X						X		X		X		X			
Vital signs	D	7.2.2.2		X	X		X	X		X	X	X	X	X	X		X			
Performance status	D	7.2.2.4		X	X						X		X		X		X			
Ophthalmic assessment	D	7.2.2.5		X				X			X		X		Xb		X			
Hematology		7.2.2.6.1		X	X		X	X		X	X	X	X		X		X			
Chemistry (predose)	D	7.2.2.6.2		X	X		X	X		X	X	X	X		X		X			
Coagulation D 7.2.2.6.3			X	If clinically indicated										•						
Urinalysis (microscopic or macroscopic)		7.2.2.6.4		X	If clinically indicated															
Pregnancy test	D	7.2.2.6.5		X	X						X		X		X		X			

	Category	Protocol Section	Molecular Pre- screening	Screeninga	Cycle 1		Cycle 2		Cycle 3		Subsequent		End of study treatment	30-day follow-up	Disease Progression follow-up every 8 weeks	Survival follow- up (every 4 months after EOT)				
Study Period			Screen	ning	Treatment EOT									EOT		Follow-up	 			
Day of Cycle				-21 to -1	1	2	8	15	16	21	1	15	1	15	1	15	≤14 days of the decision to discontinue the treatment			
Tumor response per RECIST 1.1	D	7.2.1		X									X		Day 1 of every odd cycle		X (if not done within 28 days prior)		X (only for pts. who discontinue for any reason other than progression of disease	
Study drug administration	dministration D 6.1 Continuous on a 3 weeks on 1 week off schedule c																			
12-lead ECG	D	7.2.2.7		X	X	X	X	X			X		X		X		X			
Cardiac imaging (ECHO or MUGA)	D	7.2.2.7		X							X						X			
Adverse Events	D	8.1, 8.2						Cor	ntinuo	ously	throu	ghout	the s	tudy				X		
Collection of archival paraffin blocks/slides or a newly obtained tumor sample AND pathology report	D	7.2.4.1	X (if local data not available)	X d																
Newly obtained tumor sample (if medically feasible)		7.2.4.2		Xe	X (upon disease progression)-optional															
Blood sample for assessment of circulating tumor DNA (cell free DNA) (all samples are predose)	D	7.2.4.3		X							X		X		Day 1 of every odd cycle		X (if not done within 28 days prior)			
Blood for PK (sparse PK group)	D	7.2.3.1			X	X	X	X		X	X	X	X	X	,	Day 15 Cycles 4- 6				

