#### 7.2.2.6.5 Pregnancy and assessments of fertility

All WOCBP (pre-menopausal or less than 1 year after the onset of menopause) must have a serum pregnancy test  $(\beta-hCG) \le 72$  hours before the first dose of study treatment. Additionally, a serum pregnancy test should be performed at Day 1 of each cycle and at the End of Treatment visit.

Table 9: Clinical laboratory parameters collection plan

Test Category	Test Name
Hematology	Hematocrit, Hemoglobin, Red blood cell count, Platelets, White blood cells, Differential (Basophils, Eosinophils, Lymphocytes, Monocytes, Neutrophils)
Biochemistry	Albumin, Alkaline phosphatase, ALT (SGPT), AST (SGOT), Calcium (can be corrected), Chloride, Creatinine, Blood Urea Nitrogen (BUN), Potassium, Sodium, Magnesium, Phosphate.
	Direct Bilirubin, Indirect Bilirubin, Total Bilirubin, Lipid profile (Total Cholesterol, Triglycerides), Total Protein, Urea, Uric Acid, Amylase, Lipase
Urinalysis	Macroscopic Panel (Dipstick) (Blood, Glucose, Ketones, pH, Protein, Specific Gravity).
	Microscopic Panel (Red Blood Cells, WBC)
Coagulation	Prothrombin time (PT) or International normalized ratio [INR]), Partial thromboplastin time (PTT)
Pregnancy Test	Serum hCG at screening; day 1 of each cycle, EOT and other times points

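### Table 5 holds the phosphate binder in the planned week off of every cycle without the exception for unnormalized phosphorus that Section 6.3.1 makes

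*Protocol*

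**What the plan says.** Four pieces of current protocol text bear on the binder in the planned week off.

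- **Table 5, Hyperphosphatemia (Section 6.2.1).** The week-off rule is "Phosphate binder dosing should be held during the week off BGJ398 therapy each cycle (Days 22-28". The same sentence extends the hold to BGJ398 interruptions for other adverse events. No phosphorus level is attached.
- **Table 5, the preceding sentence.** "It is recommended that phosphate binder dosing continues during BGJ398 dose interruptions for hyperphosphatemia". This concerns unplanned interruptions for raised phosphorus.
- **Section 6.3.1, Management of Hyperphosphatemia.** Once a patient has had hyperphosphatemia, the binder goes with the days on which BGJ398 is taken. In the week off the patient need not follow the diet or "take a phosphate binder during their 1-week off period unless serum phosphorus is not normalized".
- **Section 6.1.2, Ancillary treatments.** It points readers to Table 5 and allows local adaptation: "Recommendations for treatment are provided in Table 5, but should be modified as per country or institutional guidelines". Section 6.3.1 has a similar clause for local practice.

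**The concern.** Both texts share a default of no binder in the week off. They part for the patient in whom that default matters most, the one who reaches Day 22 with phosphorus still high. Section 6.3.1 foresees this patient and Table 5 does not. Table 5 is where Section 6.1.2 sends the reader, so a site working from the table alone would miss the exception.

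What is at stake is patient management and, through it, the descriptive safety summaries. The protocol calls hyperphosphatemia an on-target effect (Section 6.3.1). It reports that most phase I patients on continuous dosing at 100 mg daily or more had it, reversibly (Section 2.3). In rats and dogs, raised phosphorus went with partially reversible ectopic mineralization (Section 1.2.1.1.2). The SAP lists hyperphosphatemia and tissue calcification as adverse events of special interest (Section 2.7.2.1.2).

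**Working it through.** The plan gives no figure to reproduce. The check compares texts, with simple day counts.

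**1. Does another line of Table 5 resolve the difference?** The instruction to continue the binder applies to interruptions for hyperphosphatemia. Table 5 names the week off separately, and SAP Section 2.5.1.5 does not count the planned week off as an interruption. That SAP rule governs counting, not care, but it agrees with the table's own distinction. The line therefore protects patients already on such an interruption, who are outside this point, and not those entering the planned week off.

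**2. Can a patient reach Day 22 with raised phosphorus and no interruption?** Yes. Table 5 holds BGJ398 for phosphorus above 7.5 mg/dL "for more than 7 days despite maximal phosphate-lowering therapy", or for a single value above 9.0 mg/dL. Raised values outside those criteria are:

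- above 5.5 and up to 7.5 mg/dL, where the instruction is "Maintain dose level of BGJ398 and optimize phosphate lowering therapy as clinically indicated";
- above 7.5 and up to 9.0 mg/dL, for 7 days or fewer or without maximal therapy.

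These bands illustrate the group but do not define it. Section 6.3.1 speaks only of phosphorus that has not normalized, and the documents give no upper limit of normal. If a laboratory's limit is below 5.5 mg/dL, patients between the two are included as well.

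**3. What does each text imply for this patient?**

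| | Table 5, read literally | Section 6.3.1 |
|---|---|---|
| Phosphorus normal at Day 22 | binder held | binder not needed |
| Phosphorus raised at Day 22 | binder held | not released from binder |

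The texts differ only in the second row.

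**4. How many days?** The week off is 28 − 22 + 1 = 7 days.

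- Table 5: 7 binder-free days in an affected cycle, or 7/28 = 25% of that cycle.
- Section 6.3.1: if phosphorus normalizes on Day d (23 to 28), release covers 28 − d + 1 days. Normal on Day 23 gives 6 days and on Day 28 gives 1 day. If phosphorus stays raised all week, the figure is 0.
- Difference: from 7 − 6 = 1 day to 7 − 0 = 7 days per affected cycle.

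**5. Would the site know the phosphorus value?** The Table 7 row "Chemistry (predose" schedules chemistry on Cycle 1 Days 1, 8, 15 and 21, Cycle 2 Days 1 and 15, and Day 1 only from Cycle 3. Table 9 includes phosphate in that panel ("Potassium, Sodium, Magnesium, Phosphate"). The nominal age of the last scheduled value at Day 22, ignoring visit windows, is:

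- Cycle 1: 22 − 21 = 1 day
- Cycle 2: 22 − 15 = 7 days
- Cycle 3 onward: 22 − 1 = 21 days

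In Cycle 1 the question arises at a routine visit. In later cycles, applying the exception relies on unscheduled tests, which Section 7.2.2.6 allows.

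**The case against.** The best defense reads the two texts together: Table 5 states the general rule, and the section devoted to hyperphosphatemia qualifies it. Several points support this.

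- Section 6.3.1 withdraws a permission and does not expressly order dosing. A reader might infer that sites receive opposite instructions, but the wording does not go that far. This stands.
- The Table 5 column covers modifications at any time in a cycle, and its row for values above 5.5 and up to 7.5 mg/dL calls for optimized phosphate lowering. As extracted, the hold sentence sits beside the higher-phosphorus row. However, its reference to each cycle reads as a general rule, and the table layout may have been lost in extraction. This softens the conflict but does not settle it.
- Local practice may override Table 5, so some sites may already follow Section 6.3.1. This stands, but it gives no answer where no local rule exists.
- BGJ398 is off that week, the hyperphosphatemia is described as reversible, and holding the binder off drug plausibly guards against hypophosphatemia, which Table 5 also manages. A reader might infer that Table 5 is the unsafe text. The documents contain no data to show that. Still, Section 6.3.1 itself foresees phosphorus that stays raised in the week off.

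A further objection is that the added clause leans on unscheduled tests from Cycle 3 and on an undefined threshold. That is true, but Section 6.3.1 already carries both features; the clause only makes Table 5 agree with it.

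**Conclusion.** The inconsistency is real and minor. For a patient with raised phosphorus at Day 22 who is not on an interruption for hyperphosphatemia, Table 5 omits an exception that Section 6.3.1 contains, and no text sets precedence. This rests on reading the Table 5 hold as applying to all patients in the planned week off.

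Two larger readings are tempting and should not be drawn. A flat contrast of 7 days against none holds only if phosphorus stays raised all week. Loss of binder for a quarter of every cycle holds only if phosphorus is raised at Day 22 each time. The documents support neither as a general statement, nor any count of affected patients.

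Overall response rate, the other efficacy endpoints, the sample size and the planned analyses are unaffected. The wording is worth correcting because the correction is nearly free and protects patients with persistent hyperphosphatemia.

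**What to change.** At the next planned amendment, add to the Table 5 sentence on the Days 22-28 binder hold: *unless serum phosphorus is not normalized (see Section 6.3.1)*. No other change is needed.

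The cost is one clause in one table row, with no new visits, tests or analyses. Section 12.1 requires a written amendment with IRB/IEC/REB approval, and Health Authority approval where required. The change should therefore travel with an amendment made for other reasons.

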# 1.2.1.1.2 Safety pharmacology and toxicology

BGJ398 showed no evidence of *in vitro* genotoxicity in Ames and chromosome aberration tests and no evidence of phototoxicity in a 3T3 photo-cytotoxicity test. *In vitro* safety pharmacology assessment of BGJ398 revealed a decrease in human Ether-à-go-go-related gene (hERG) channel activity with an IC50 of 2.0 μM (1121ng/ml). *In vivo* safety pharmacology studies in rats and dogs did not reveal any effects on central nervous or respiratory systems and on hemodynamic or electrocardiographic parameters, respectively.

In repeated dose (oral gavage; up to 4-weeks) toxicity studies, BGJ398 did lead to increases in serum FGF23 and serum phosphorous associated with partially reversible ectopic mineralization (kidney, lung, vascular and digestive systems) along with largely reversible changes in renal function parameters and bone growth plate thickening / retention of the primary spongiosa in rats ( $\geq 10$  mg/kg/day) and dogs ( $\geq 10$  mg/kg/day). These effects were deemed to be on-target effects mediated by pharmacological inhibition of FGFR.

In rats, corneal changes were found upon 4 weeks of BGJ398 treatment consisting of irreversible, slight bilateral opacity with dose-dependent incidence, as assessed by in vivo ophthalmology. The clinical/ophthalmoscopic finding was associated with reversible, diffuse epithelial keratopathy at the highest dose of 10 mg/kg. In the 2-week rat toxicity study, doses of 20 mg/kg/day did lead to vasculopathy associated with moribundity after 6 administrations.

In dog toxicity study, minimal, fully reversible retention of the primary spongiosa and minimal increase in mineralization in lung and kidney without observed functional impairment were observed.

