## 6.2 Dose modifications

# 6.2.1 Dose modifications and dose delay

For patients who do not tolerate the protocol-specified dosing schedule, dose adjustments are permitted in order to allow the patient to continue the study treatment. All dose modifications should be based on the worst preceding toxicity (Table 5, Table 6). Dosage changes must be recorded on the Dosage Administration Record CRF.

The following guidelines should be applied.

Each patient will be allowed 3 dose reductions according protocol-specified dose modifications for AEs. A QED medical monitor or designee approval is required for the third dose reduction (Table 4).

Following resolution of toxicity to baseline or  $\leq$  Grade 1, treatment is resumed at either the same or lower dose of study drug as per the criteria in Table 5. If treatment is

resumed at the same dose of study drug, and the same toxicity recurs with the same or worse severity regardless of duration, dose must be reduced to the next lower dose level. If treatment is resumed at the lower dose of study drug, and the same toxicity recurs with the same or worse severity, the patient should have a second dose reduction.

Patients who discontinue study treatment for a study related adverse event or an abnormal laboratory value must be followed as described in Section 6.2.2.

Study drug must be permanently discontinued for a delay of >14 days and may only be restarted with written permission of a QED Therapeutics' medical monitor if (1) the delay was not due to an AE that requires permanent study drug discontinuation as provided in Table 5, and (2) the patient has not met other criteria requiring study drug discontinuation in Section 7.1.4, and it is the Investigator's opinion that no safety concerns are present.

Table 4: Dose reduction table

Dose reduction				
	Starting dose level 0	Dose level -1	Dose level -2	Dose level -3
BGJ398	125 mg	100 mg	75 mg	50 mg a

Dose reduction to 50 mg requires QED Therapeutics medical monitor approval. Details are provided in the text above.

 Table 5:
 Criteria for interruption and re-initiation of BGJ398 treatment

Worst Toxicity CTCAE v4.03 Grade (unless otherwise specified)	Dose Modifications any time during a cycle of therapy
Cardiac disorders	
Cardiac - Prolonged QTcF interval	

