2.7.2.1.2 Data Analysis

AE Summaries

AE summaries will include all AEs occurring during on-treatment period, i.e. treatment emergent AEs. Treatment emergent AEs (TEAEs) include all AEs that started on or after the first administration day of study treatment and up to last study administration day of study treatment +30 days. All AEs collected in the AE (e)CRF page will be listed along with the information collected on those AEs, eg, AE relationship to study drug, AE outcome, etc. Treatment-emergent AEs will be flagged in the listings.

TEAEs will be summarized by number and percentage of subjects having at least one TEAE, having at least one TEAE in each primary system organ class (SOC) and for each preferred term (PT) using MedDRA coding. A subject with multiple occurrences of an AE will be counted only once in the respective AE category. A subject with multiple CTCAE grades for the same preferred term will be summarized under the maximum CTCAE grade recorded for the event. AE with missing CTCAE grade will be included in the 'All grades' column of the summary tables.

In TEAE summaries the primary system organ class will be presented alphabetically, and the preferred terms will be sorted within primary SOC in descending frequency. The sort order for the preferred term will be based on their frequency in FAS. The following TEAE summaries will be produced by treatment and by FGFR2 fusion/translocation status:

- Overview of TEAEs and deaths (number and % of subjects who died from fatal TEAE, number and % of subjects with any TEAE, any treatment emergent serious AE, any TEAE leading to dose reductions/interruptions, TEAE leading to discontinuation of study treatment)
- All TEAEs by SOC and PT and worst grade
- Treatment related TEAEs by SOC and PT and worst grade
- Grade 3 or 4 TEAEs by SOC and PT and worst grade
- Treatment emergent serious AEs (SAEs) by SOC and PT and worst grade
- Treatment emergent serious treatment-related AEs by SOC and PT and worst grade
- TEAE with fatal outcome by SOC and PT and worst grade
- TEAE leading to study treatment discontinuation by SOC, PT and grade
- TEAE leading to dose interruption/adjustment by SOC, PT and grade
- TEAE leading to treatment discontinuation by SOC and PT and worst grade
- TEAE requiring additional medication or therapies by SOC and PT and worst grade
- All TEAEs by PT by descending order of frequency
- Treatment related TEAEs by PT by descending order of frequency

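### Table 5 gives two opposite actions, permanent stop or restart one level lower, for a Grade 4 non-retinal eye event that resolves within 14 days

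*Protocol*

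**What the plan says.** The relevant part of Table 5 in Protocol 6.2.1 is headed "Eye Disorders (confirmed by ophthalmic examination") and has two sub-headings.

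- *Retinal disorders*, third row (Row A below): the trigger is retinal vein occlusion of any grade, together with "Grade 4 central serous retinopathy and central serous retinopathy-like events, and Grade 4 other eye disorders". The action is to "discontinue patient from study treatment", and no restart is described. The protocol glossary defines study treatment discontinuation as a permanent stop.
- *Retinal disorders*, second row (the Grade 3 companion): besides Grade 3 central serous retinopathy, it covers "any other Grade 3 eye disorders". The drug is held until Grade 1 or below, then reduced one level if that takes no more than 14 days and discontinued if it takes longer.
- *Other ocular/visual toxicity*, its only row (Row B below): the trigger is Grade 3 or higher. The drug is held until Grade 1 or below. Then: "If resolution within ≤14 days, ↓ 1 dose level"; if resolution takes longer, the drug is discontinued.

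The general instruction in Section 6.2.1 reads "All dose modifications should be based on the worst preceding toxicity (Table 5, Table 6"), and the note closing Table 5 repeats it. The text on resuming treatment after recovery refers back to Table 5.

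**The concern.** Row A names eye disorders other than central serous retinopathy at Grade 4. Row B includes Grade 4 because it has no upper grade limit. A Grade 4 non-retinal event that settles in time satisfies both triggers, and the two actions are opposite: never dose again, or dose again at a lower level.

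This rule governs re-exposure after a severe eye event. Eye toxicity is anticipated for this drug. Protocol 1.2.1.1.2 describes corneal opacity in rats, slight but irreversible, "associated with reversible, diffuse epithelial keratopathy at the highest dose of 10 mg/kg". The protocol schedules slit-lamp examinations, and the SAP makes eye disorder an adverse event of special interest.

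Three consequences follow from an unranked overlap.

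- Two sites that both follow Table 5 literally could treat the same patient differently.
- A patient restarted under Row B could be classed as a deviation by someone reading Row A. SAP 2.4 has a reportable category for patients who met withdrawal criteria but were not withdrawn, and Protocol Section 12 allows no authorised deviations.
- SAP 2.7.2.1.2 plans a table of "TEAE leading to study treatment discontinuation by SOC, PT and grade" and a separate one for events leading to dose interruption or adjustment. The same event could be counted differently depending on which row the site applied.

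**Working it through.** No statistical calculation applies. The check applies both blocks to one type of event, a non-retinal eye event, at each grade and resolution time that the rows distinguish.

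**Inputs**

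- Row A, its Grade 3 companion and Row B: Table 5, Protocol 6.2.1.
- Dose levels: Table 4, Protocol 6.2.1 (125, 100, 75 and 50 mg; the last needs medical monitor approval).
- Meaning of discontinuation: protocol glossary (permanent).

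**Case by case**

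| Grade | Resolution to Grade 1 or below | *Retinal disorders* block (other eye disorders) | *Other ocular/visual toxicity* block | Agree? |
|---|---|---|---|---|
| 3 | 14 days or less | Hold, then reduce one level | Hold, then reduce one level | Yes |
| 3 | More than 14 days | Discontinue | Discontinue | Yes |
| 4 | 14 days or less | Discontinue | Hold, then reduce one level | **No** |
| 4 | More than 14 days | Discontinue | Discontinue | Yes |

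The blocks disagree in 1 of 4 cases. In that case a patient at the starting dose of 125 mg goes to either 0 mg permanently or 100 mg.

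**Does anything else in the protocol rank the two rows?**

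1. *Worst preceding toxicity.* This selects the grade to act on. Here the grade is 4 under both rows, so it cannot choose between them.
2. *The rule on delays over 14 days (6.2.1).* It does not apply, because the disputed case resolves within 14 days.
3. *The general pattern of Table 5.* It points both ways. Grade 4 neutropenia, anemia, thrombocytopenia and fatigue allow resumption. Grade 4 diarrhea, vomiting and AST/ALT elevation do not, and the catch-all row for other clinically significant adverse events discontinues at Grade 4.
4. *Section 7.1.4.* It requires discontinuation when an adverse event substantially changes the individual risk-benefit balance. That is a case-by-case judgement and does not say whether Table 5 permits a restart.

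None of the four resolves the overlap.

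**The case against.** The strongest counter-argument is the layout. Row A sits under *Retinal disorders*. If each row is limited by its own sub-heading, other eye disorders means other retinal disorders, a corneal event falls only under Row B, and there is no conflict. This reading is possible and gives each block its own purpose. It does not remove the problem, because the words chosen are eye disorders, not retinal disorders, and the companion row uses the similarly broad "any other Grade 3 eye disorders". On this reading a Grade 4 non-retinal eye event may be restarted, whereas the table's catch-all row discontinues at Grade 4. A careful site could adopt either reading.

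The other objections concern emphasis, and most of them stand.

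- The catch-all row and several organ-specific rows discontinue at Grade 4, so the table leans somewhat towards the cautious row.
- The rat findings do not show that a Grade 4 human event settling within 14 days is likely. They include an irreversible component, and neither document reports such an event.
- Safeguards exist: at least weekly follow-up of interrupted patients, specialist consultation where needed, ongoing sponsor safety review and investigator teleconferences. Even Row B requires recovery to Grade 1 or below and a lower dose.
- The affected tables are descriptive and would record what was actually done.

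These points limit the likely harm. They do not say which row governs.

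**Conclusion.** The contradiction is real as the table is written. It is confined to Grade 4 non-retinal eye events that settle to Grade 1 or below within 14 days, one of the four cases above. The outcome there is a permanent stop or a restart one dose level lower.

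The conclusion rests on reading Row A by its words rather than by its sub-heading. The sub-heading reading cannot be excluded as the sponsor's intent, but the text does not state it. The number of patients affected is unknown and probably small. The primary analysis of overall response rate is not touched. The point deserves correction because it concerns re-exposure after a severe eye event and costs almost nothing to settle.

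**What to change.** In Table 5, change the grade entry for *Other ocular/visual toxicity* from Grade 3 or higher to Grade 3 only. Grade 4 eye events then lead to discontinuation on either reading: through Row A if it covers all eye disorders, or through the catch-all Grade 4 row for clinically significant events if Row A is retinal only. Grade 3 handling does not change. Because the Grade 4 wording would still sit under the retinal sub-heading, the site notification should state plainly that it applies to all eye disorders.

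If the sponsor intended hold-and-reduce for non-retinal events, leave Row B alone. Instead reword the Grade 4 entry in Row A, and the matching phrase in its Grade 3 companion, to refer to other retinal disorders.

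The cost of the main fix is one table entry and a notification to sites; the alternative rewords two entries. Neither needs extra patients or data.
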